 - m. Number and proportion of screened negative pediatric contacts eligible for preventive therapy
 - n. Number and proportion of pediatric patients started on preventive therapy of those who are eligible for preventive therapy
 - o. Number and proportion of pediatric patients on preventive treatment who completed therapy

2. Secondary Objectives

- a. To determine the effect of the CaP TB project on the above TB service indicators and clinical outcomes compared to baseline (standard of care) in a subset of project sites.
- b. Utilize the evidence generated from this program evaluation to support strategic recommendations to improve pediatric TB care.

- c. Utilize clinical aggregated data generated by this study to inform cost-effectiveness analysis of pediatric TB interventions implemented by CaP TB project that can contribute informing childhood TB planning and strategic allocation of financial resources
- d. Utilize evidence generated from this program to assess the impact of measures enforced to control the COVID -19 pandemic on accessibility and availability of pediatric TB services

III. Expected Outcomes of the Study

The main expected outcome of CaP TB project is to reduce morbidity and mortality associated with pediatric TB^{xxx} by reducing the pediatric TB diagnostic and treatment gap, increasing coverage of quality assured TB treatments, as well as scale up of TB preventive therapy through innovative models of care for pediatric TB that focus on integration and decentralization. We expect that this program evaluation will document a positive impact of the CaP TB model, with estimated two-fold increase in case detection and four-fold increase in pediatric patients started on TB preventive therapy based on project target estimates. The evaluation of the CaP TB project will allow for dissemination of the results and further uptake of proven models by other countries.

IV. Study Design

We are planning a pre-/post-project (quasi experimental) intervention evaluation. The population will include all pediatric patients (0-14 years of age) who present to a CaP TB project site in any of the 10 countries and receive TB services (including screening, diagnosis and treatment for active TB, and provision of TB preventive therapy).

A. Methodology

[figure not shown]
1. Description of the CaP TB Project

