While most of the CaP TB project will be implemented in public facilities, in some EGPAF-supported countries, EGPAF has worked with the private sector, including faith-based clinics. EGPAF will also support select private health facilities that EGPAF currently supports to adopt CaP TB project interventions, including integration of care and improved models of care for case finding and uptake of TB preventive therapy. In India, SAATHII has focused much of its work supporting the private sector through public-private partnership models. These models have shown considerable promise to improve TB care in India and similar contexts and SAATHII has utilized this model to improve pediatric care in the private sector in India.^{XXXI}

Initially, CaP TB will be implemented in approximately 15-20 purposefully selected and diverse sites per country for the first 2 years of the project (October 2017-October 2019) to refine approaches, determine costs, and inform a second phase of expanded implementation to prove scale-ability, avoid interventions becoming stuck in the pilot phase, and bridge to scale up. Data gathered will be used to demonstrate the effectiveness and feasibility of innovative interventions. During the last six months of this intensive monitoring phase, EGPAF will analyze the results and lessons learned from early implementation of these innovative models of care. Results will be discussed with key in-country and international stakeholders in order to help refine the models and plan for a period of expanded implementation.

EGPAF will then enter into a period of expanded implementation that will help to prove and catalyze scalability and bridge to transition. The number of sites chosen for the expanded implementation phase was selected to ensure sufficient strength of evidence to induce catalytic change nationally, be generalizable and build a good basis for eventual transition and scale up. Thus, within each country, EGPAF's site selection aimed to include: 1) Multiple types of sites including different health facility levels; 2) varying health entry points (e.g. nutrition centers, sites

with pediatric inpatient wards, etc.); 3) diverse geographic setting and ease of access to health facilities; and 4) different population types (including key populations such as refugee populations, fisher folk). Depending on the size of the country and the diversity of the contexts within each country, this resulted in a varying number of sites per country.

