 - GeneXpert diagnostic assays (i.e Xpert MTB/RIF Ultra)^{xxxii}
 - Quality-assured pediatric dispersible formulations of fixed dose isoniazid-rifampicin-pyrazinamide and rifampicin-isoniazid as well as ethambutol single formulation for the treatment of active TB disease;

- Quality-assured pediatric formulations of dispersible isoniazid single formulation and fixed dose rifampicin-isoniazid for preventive therapy^{XXXIII}.
- Supporting the introduction and use of e-/m-health technologies (i.e connectivity solutions, SMS-reminders) to strengthen performance of TB screening at household level, linkage to care and/or patient's treatment adherence strategies

Drugs and diagnostics used in CaP TB must have approval from a stringent regulatory agency or be recommended by the Global Fund ERP, the WHO prequalification program or WHO Global TB program and be registered by the country national regulatory authority or have an exemption for import and routine use in the country. Cepheid recommends that gastric aspirate (GA) samples tested on the Cepheid GeneXpert platform be centrifuged to improve yield. As some of our Xpert testing sites will not have access to the appropriate centrifuge and infection control equipment, we will use direct GA specimens without centrifugation for Xpert testing. Testing without a concentration step (achieved through centrifugation) may reduce the sensitivity of Xpert testing for this specific sample type. It will not affect specificity. As the sensitivity of GA even with a centrifugation step is estimated to be 83% according to a WHO meta-analysis, WHO guidelines^{XXXIV} recommend that a negative result from a GA sample tested on Xpert not be used to definitively rule out TB. As the sensitivity from testing without a centrifugation step may be lower, we will stress in our trainings that a negative result from an Xpert test on GA does not rule out TB. This practice will be reviewed with the National TB Program before implementation.

3. Duration of the Project

Data collection of pre-intervention retrospective baseline data collection will take place in the months prior to or immediately after the start of CaP TB project interventions. Post-intervention data collection will take place once the facility is enrolled in CaP TB and will be on-going over the course of the project (through September 30, 2021). It is expected that most countries will begin enrolling pilot facilities by September 2018.

V. Description of Project Evaluation

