The CaP TB model represents one potential way of improving the care of pediatric TB. However, it will be important to measure this model's effect on key service and clinical indicators related to pediatric TB in order to help guide future programming and resource prioritization. In order to describe the effect of the CaP TB model on these indicators, we plan a pre- and post-intervention evaluation in all project countries. We have chosen this pragmatic approach to allow us to compare the outcomes after we begin CaP TB implementation with the same indicators baseline (pre-implementation). This can help us define the effect of our specific project on the project evaluation indicators. As this is an evaluation of program implementation a randomized approach would not be feasible for both programmatic and financial reasons. We do recognize that secular trends may affect our outcomes, but we feel that the duration of the evaluation (over several years) and the large size and multi-country nature will help to mitigate that risk.

A. Pre-intervention Evaluation- Baseline assessment

In each country, a pre-intervention retrospective data collection will take place in a sub-set of project sites.

This data collection activity will:

1. Capture data that will answer the TB service indicators and clinical outcomes listed in the primary objectives.
2. Capture key data points that will be needed to estimate project targets

The main objectives of the CaP TB interventions are:

- to increase the number of children diagnosed with TB
- To increase the number of children who are started on and complete DS-TB treatment
- To increase the number of children who are started on and complete TB preventive therapy.

Key indicators that will be used to monitor project interventions and assess impact will therefore be:

- Number of pediatric cases diagnosed with active TB disease
- Number and proportion of pediatric DS-TB cases who achieve treatment success
- Number and proportion of pediatric patients started on preventive therapy of those who are eligible for preventive therapy
- Number and proportion of pediatric patients on preventive treatment who completed therapy

Data sources for these indicators during the pre-intervention phase are described in Table 1.

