Location of activity	10-20 purposively selected pilot sites in each country, for a total of up to 200 sites across all ten countries. Sites will be selected based on geography (urban vs rural) and health facility level. We estimate that 12 months of data will be sufficient to appropriately assess the indicators from the primary objectives under standard of care conditions. The overall sample size in each country and per facility sample size will vary greatly by facility level, pediatric population density and indicator. However, we estimate that we will collect data for at least 5 children with presumptive TB in each clinic.	Up to 70 sites in each country for a total of up to 700 sites across all ten countries.
Timing	15-20 CaP TB pilot sites in each country	All CaP TB sites across 10 countries (up to 700 sites)
Method	Retrospective data collection will occur upon site selection. It is estimated that the retrospective data collection for all sample project sites in a given country will take six to ten weeks.	Data collection will begin when each site begins implementation of CaP TB and will go on through the end of the project
	Data abstraction of TB registers, HIV registers, PMTCT registers and other relevant logbooks	Data abstraction from clinic attendees registers, Pediatric TB Intensified Case Finding Screening Tool, CaP TB Pediatric TB Form, TB treatment register, TB preventive therapy register and other TB registers and logbooks as needed

Informed Consent documents	Informed consent waiver to be requested	Informed consent waiver to be requested
Data collection tool	Baseline data abstraction tool	Pediatric TB Intensified Case Finding Screening Data Abstraction Tool and CaP TB Database Entry Tool

IX. Data Management and Statistical Analysis

Quantitative de-identifiable data extracted from the source documents will be coded and entered directly into a database that will be designed specifically for the project and stored on a secure cloud server. Data will be aggregated in the database and entered into an electronic dashboard that will demonstrate the data standardized to project indicators and data elements. Frequencies will be calculated for each response and descriptive statistics will be calculated.

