Project data sample size: As this is a project evaluation, no specific sample size has been calculated. However, we estimate that the project will increase case detection by 2-fold and result in an additional 16,471 pediatric TB cases being treated.^{xxxix} This is based on an assessment of the number of children we project to screen (both HIV positive and HIV negative) in our project sites throughout the project. From the literature, we estimate that approximate Number Needed to Screen (NNS) to identify 1 TB case is 41 children. Assume that Number Needed to Screen (NNS) to identify 1 TB case is 41 (estimated NNS when symptom based screening is the only primary screening done)^{xl, xli}. Preventive treatment coverage is estimated to increase by four-fold, with an additional 52,317 children to be initiated on preventive therapy. This is based on the estimated number of child TB contacts we will identify through contact tracing plus HIV-infected children who qualify for preventative treatment.

To compare pre- and post-intervention outcomes, we will use either the ratio of the two proportions (relative risk) or the difference between the two proportions (risk difference). We will use Z-tests to assess the statistical significance of the estimated effect of CaP TB.

For measuring turn-around-time (TAT) between when a child is identified as a presumptive TB case and when the child is diagnosed with TB and the TAT between when a child is diagnosed as a presumptive TB case and when the child initiates TB treatment, if the TATs are approximately normally distributed, we will use the paired t-test to assess for statistical significance, otherwise we will use the Wilcoxon rank sum non-parametric test.

A. Quality Assurance

All data collectors will be trained in quantitative data collection by EGPAF staff. Prior to training, all data sources, abstraction and collection tools and procedures will be reviewed and tested. The HQ EGPAF team will provide on-going support to in-country teams throughout program implementation and all data collection activities.

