Data abstracted or collected for this evaluation will be used to 1) Estimate project targets; 2) evaluate the effect of CaP TB as compared to standard of care pediatric TB services as well as to 3) assess the effects of CaP TB during the continued scale up phase (years 3 and 4). Data will be abstracted/collected, analyzed and reviewed on a routine basis to inform program implementation and quality improvement activities, target setting and adjustments, internal and external reports, abstracts, presentations and international guidelines.. Findings will be shared across the project countries, with MOHs, with other implementing partners, with Unitaaid and the WHO and the international community through semi-annual reports to the funder (Unitaid), grey literature, and publications in peer-reviewed journals, meetings and presentations. In order to perform cost-effectiveness analysis, aggregated clinical data will be abstracted and shared with University of Sheffield. Unpublished data analysis and databases might be shared with WHO and with WHO’s collaborators that will be commissioned to compile and assess the evidence needed to support revisions of guidelines and policy formulation. Findings will also be shared through EGPAF data dashboards and website.

Data presented as part of study findings in papers or at conferences will not include any participants' names, IDs or study identifiers. Only the names of project countries will remain identifiable if required.

XIII. Problems Anticipated

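### The CaP TB pre/post effect is adjusted for neither calendar time nor COVID-19, and the plan counts duration and size as protection against secular trends, which they are not in an unadjusted comparison

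*Combined protocol and SAP*

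**What the plan says.** The goal in section II.A includes comparison with baseline. Secondary objective a in II.B.2 is the effect of the project "compared to baseline (standard of care) in a subset of project sites".

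Section V acknowledges that secular trends may affect the outcomes. Its answer is that "we feel that the duration of the evaluation (over several years) and the large size and multi-country nature will help to mitigate that risk". No analytic step follows.

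Section IX gives the analysis: "we will use either the ratio of the two proportions (relative risk) or the difference between the two proportions (risk difference"), and "We will use Z-tests to assess the statistical significance of the estimated effect of CaP TB". It contains no time term, no comparison sites and no mention of COVID-19.

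The baseline is a 12-month retrospective window (V.A). Post-intervention data collection "will be on-going over the course of the project (through September 30, 2021") according to IV.A.3. Table 3 says the same: "Data collection will begin when each site begins implementation of CaP TB and will go on through the end of the project". These passages define when data are collected. No passage defines which post months enter the comparison. Section IV.A.1 describes a first implementation phase "for the first 2 years of the project (October 2017-October 2019"). Section XII lists the evaluation against standard of care as one use of the data and, as a separate use, to "assess the effects of CaP TB during the continued scale up phase (years 3 and 4").

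Section VII.B plans a time-series analysis of COVID-19 measures as a separate question. Its result does not enter the estimate of the CaP TB effect.

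**The concern.** A pre/post contrast without a time term estimates the project effect plus whatever else changed between the two periods. If all ten countries share a background trend, a longer post period moves its midpoint further from the baseline, so the bias grows. A larger sample only narrows the interval around the biased value, so a null effect is more likely to be declared significant. Averaging over ten countries can dilute trends that differ between countries, but not a common one. Two of the three features named in section V therefore work against the claim made for them.

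COVID-19 is a shared shock that probably covers about half of the post period and can hide part of a real rise in counts. The documents therefore contain possible influences in both directions, and the reader of the final estimate cannot tell which dominates. This matters most for indicators where a modest change is plausible, such as treatment success or completion of preventive therapy, and for the P values attached to them.

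**Working it through.** The plan states no sample size, power or significance level for this comparison, so it has no figure to reproduce. The values below illustrate size and are labelled where assumed.

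**Inputs from the documents.** Baseline of 12 months (V.A). Pilot sites enrolling by September 2018 in most countries (IV.A.3), and data to September 2021, so 37 calendar months. Table 3 gives 10-20 baseline sites in each of ten countries and at least 5 children with presumptive TB per clinic: 100 × 5 = 500 to 200 × 5 = 1,000 baseline children.

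**Assumed.** Background rise g of 2%, 5% or 10% a year; baseline proportion p0 of 10% or 40%; two-sided 5% test; independent children; baseline ending at site start; COVID-19 measures from March or April 2020.

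**1. Trend bias with no true effect.** Ratio = mean of (1+g)^(t/12) over the post months ÷ the same mean over the 12 baseline months.

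| Post months | g = 2% | g = 5% | g = 10% |
|---|---|---|---|
| 12 | 1.02 | 1.05 | 1.10 |
| 37 | 1.04 | 1.11 | 1.22 |

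If the baseline ends 6 months before start, the 5% values become 1.08 and 1.13. Lengthening the post period raises the bias in every column.

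**2. Z-test rejection with no true effect, 37 post months.** n2 = n1 × 37/12; p1 = p0 × ratio; z = (p1 − p0)/√[p̄(1 − p̄)(1/n1 + 1/n2)], where p̄ is the pooled proportion; rejection = Φ(z − 1.96) + Φ(−z − 1.96).

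Worked case: g = 5%, p0 = 0.40, n1 = 500, n2 = 1,542. Then p1 = 0.442, p̄ = 0.432, SE = 0.0255, z = 1.66, and rejection is 38%. With n1 = 1,000, z = 2.34 and rejection is 65%. The same trend is more significant with more children.

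| Rise a year | Proportion | Rejection, n1 = 500 to 1,000 |
|---|---|---|
| 2% | 10% | 6-7% |
| 2% | 40% | 10-15% |
| 5% | 10% | 10-15% |
| 5% | 40% | 38-65% |
| 10% | 40% | 93-100% |

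Clustering by site is ignored here.

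**3. COVID-19.** From September 2018, 18 months precede March 2020 and 19 precede April 2020. That leaves 19/37 = 51% or 18/37 = 49% of post months under measures. For counts, with an assumed drop x of 20-40% in those months, a true ratio of 2.0 reads 2 × (1 − share × x): from 2 × (1 − 0.51 × 0.4) = 1.59 to 2 × (1 − 0.49 × 0.2) = 1.81.

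**4. Scale.** The midpoints of a 12-month baseline and a 37-month post period lie 6 + 18.5 = 24.5 months apart, about two years. A trend alone would need 2^(1/2) − 1 = 41% a year to produce a doubling, and 4^(1/2) − 1 = 100% a year to produce a four-fold rise.

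**5. Price of a pre-COVID window.** Assuming independent months of equal variance, the standard error relative to the full period is √(1/12 + 1/18)/√(1/12 + 1/37) = 1.12, or 1.11 with 19 months. For completion indicators with 6-month treatment, 12-13 start months remain against 31 (37 − 6), and the ratio is 1.18-1.20. A two-fold effect reached linearly over 12 months averages 1.67-1.68 in the pre-COVID window and 1.84 over 37 months.

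**6. Price of a trend model.** Least squares on the log scale used a linear trend, a step at CaP TB start and a step at the COVID-19 date. It was applied to that same gradual two-fold rise with no background trend and no COVID-19 drop. The fitted CaP TB step is 1.26-1.28 (1.13-1.17 with a 6-month baseline gap), and the model also fits a COVID-19 step of 0.88-0.91 that does not exist. Its standard error is 1.5-1.6 times that of the simple pre-COVID difference (1.9-2.0 with the gap).

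**The case against.** The limitation is disclosed, the plan explains why randomization was not feasible, and its wording claims only partial help. The comparison is a secondary objective; the primary objective is descriptive. All of this is true and limits the severity. It does not rescue the reasoning about size and duration, and comparison with baseline is also part of the stated goal.

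Section XIV foresees a statistical analysis plan, where a window and a time adjustment could be set. That stands: its content is not in the documents, and the fix could be placed there.

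A reader might infer that the comparison window is wide open and could be picked after results are seen. The documents do not support that much. The post period runs to the end of the project in two places, and section V compares outcomes after implementation begins with baseline, so the natural reading is all post months. October 2019 marks an implementation phase, not an analysis cut-off. What remains is that no passage states the window, and the list in section XII could be read as a split.

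A reader might also take 38-65% as the false-positive rate of the plan. It belongs to one assumed trend and one assumed proportion; other plausible values give 6-7% or 93-100%.

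Finally, duration is not useless: a long series helps to estimate a trend once calendar time is modelled. Section IX does not model it.

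**Conclusion.** The point holds. The effect estimate is unadjusted for calendar time and for COVID-19, and section V credits duration and size with help that they do not give in such an analysis. Under the assumptions shown (no true effect, 37 post months, baseline ending at start), the spurious ratio is about 1.04 to 1.22 for background rises of 2% to 10% a year. For counts, an assumed 20-40% COVID-19 drop would make a true doubling read 1.6-1.8. Trend size, proportion, size of the drop and date of the measures are not in the documents.

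It would go too far to say that trends could explain the expected two-fold or four-fold rises, or that the estimate is biased in a known direction. The first would need trends of about 41% and 100% a year, and the second cannot be settled because the two influences may oppose each other. The change should be made, but the finding does not invalidate the evaluation.

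**What to change.** 1. **Section V.** Remove size as a mitigation. Say that duration helps only where calendar time is modelled, and that the multi-country scope may dilute local trends. State that the pre/post difference includes any trend shared across the countries.

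2. **Section IX, or the analysis plan foreseen in XIV.** State that the main comparison uses all post months to September 2021 in the sites with baseline data. Next to it, report the same comparison limited to post months before each country's first COVID-19 measures. For the completion indicators, assign months by treatment start. End the pre-COVID window one treatment duration before the measures date, taking the duration from each country's guidance, because IV.A.1 leaves it to national guidance (6 months where the statement in V.A applies).

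3. **Optional sensitivity analysis, only for indicators with dated baseline records.** Fit a site-month model with site effects, a calendar trend, a CaP TB step and a COVID-19 step. State beforehand that 12 baseline months identify the trend weakly, and that gradual uptake will appear as a smaller CaP TB step and a spurious COVID-19 step (working, item 6). A small fitted step is therefore not evidence of no effect.

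**Cost.** Text, analysis time and one measures date to look up per country; no new patient data. The pre-COVID comparison has a standard error about 1.11-1.12 times that of the full period (1.18-1.20 for completion indicators with 6-month treatment) and catches less of a gradual rise. It also remains exposed to any trend before COVID-19, which is why it stands beside the main comparison and does not replace it.

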In each site, trained data collectors will retrospectively extract data from appropriate registers, logs, and in some cases patient files, for a period of 12 months starting 6 or more months before the start date of data extraction. This time frame has been selected in order to allow to accurately measure indicators on treatment completion for both drug-sensitive TB treatment and preventive therapy (treatment lasts 6 months in both cases). In certain cases, the data sampling frame will start more than 6 months before the data extraction if CaP TB interventions had started during the sampling frame. Thus the sampling frame was chosen so that the end date of retrospective pre-intervention data abstraction would be before the start of any intervention to ensure that the baseline data was not affected by the early activities. For some indicators, baseline data will not be available in existing registers or logbooks. Data collectors will extract data from all pediatric entry points within the facility, including MNCH, HIV, nutrition and other relevant pediatric health care entry points. Only required variables will be abstracted and entered into the password-protected computers. Data with the patient date of birth (DOB), patient ID (if any), TB treatment ID and preventive treatment ID will be collected. The patient ID (if any), TB treatment ID and preventive treatment ID will all be encrypted before being uploaded into the CaP TB Database Entry Tool. DOB will be abstracted in order to facilitate tracking across registers if needed, as well as for data quality assurance purposes. This information will only be used to link registers. Only de-identified patient data will be abstracted into our global project

database. No other unique identifiers such as contact details of the children or their caregiver will be abstracted from the registers. Data from included pediatric patients will be extracted from the registers and recorded in the CapTB Baseline Data Abstraction form from where the data will be entered into a CaP TB Database Entry Tool (Excel-based and/or Web/mobile App-based) developed for pre-and post-intervention data , in a password protected computer and/or Android device (See Annex A: CapTB Information System).

The target population for the pre-intervention assessment is the records of any pediatric patient (0-14 years of age) who attend one of the sub-set of pilot sites in any of the 10 CaP TB countries who receive TB services. TB services include:

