- Screening for TB (clinical symptoms or signs)
- Receiving services (such as contact tracing) as a result of being a contact of a TB index case
- Clinical diagnostic assessment for TB
- Microbiologic diagnostic assessment for TB
- Treatment for active TB
- TB preventive therapy

Data collection of pre-intervention baseline data will take place prior to the start of CapTB interventions or immediately after, ensuring that the calculated data abstraction period does not overlap with any of the early project interventions. Data collection in each site may last up to 4 days and in some cases data collection may last several days longer.

VI. Evaluation Design and Methods

CaP TB implementation data will be collected by project-specific data collection tools and/or from existing registers. Whenever possible, the CaP TB data collection will use existing site level data collection tools to gather the data for the project. However, where such tools do not exist or the tools have gaps to capture all the necessary indicators, we will introduce project-specific data collection tools, the Pediatric TB Intensified Case Finding Screening Tool (ICF tool), the CaP TB Pediatric TB Form and any other form that may evolve as we learn lessons from project implementation.

Use of project-specific data collection tools

As part of the CaP TB intervention, healthcare workers will fill out a Pediatric TB Intensified Case Finding Screening Tool (ICF tool). This tool has no identifying information and will provide information on 1) number of children screened for TB in each healthcare entry point (e.g. pediatric ward, outpatient department, MNCH clinic, and nutrition clinic); 2) sex of the child; 3) age of the child; 4) if the child has any signs of symptoms concerning for TB (according to WHO guidance); 5) if the child is a contact of a TB case; and 6) the date of screening. The forms are also color coded according to the healthcare entry points where children are seen (White= MCH/PMTCT; Blue= outpatient department; Pink= Nutrition; Yellow= Pediatric Ward, Other=to be decided). See Attachment: Pediatric TB Intensified Case Finding Screening Tool.

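### The baseline frame must end before CaP TB launch, but baseline treatment courses need not, so treatment success and preventive-therapy completion can be partly exposed at sites extracted after launch

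*Combined protocol and SAP*

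**What the plan says.** Section V.A of the combined protocol and SAP sets two timing conditions for the retrospective baseline, each tied to a different date.

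- **Tied to extraction.** Data are taken "for a period of 12 months starting 6 or more months before the start date of data extraction". The reason given is outcome maturity: "This time frame has been selected in order to allow to accurately measure indicators on treatment completion", since "treatment lasts 6 months in both cases".
- **Tied to launch.** There is an exception: "In certain cases, the data sampling frame will start more than 6 months before the data extraction if CaP TB interventions had started during" the frame. The guard is then "Thus the sampling frame was chosen so that the end date of retrospective pre-intervention data abstraction would be before the start of any intervention", with the stated aim of keeping early activities from affecting the baseline. The end of V.A repeats the guard as "ensuring that the calculated data abstraction period does not overlap with any of the early project interventions".

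Sections IV.A.3 and V.A allow the extraction work to take place either before or immediately after CaP TB starts. V.A lists four key indicators for judging impact. Two are end-of-course outcomes: treatment success in DS-TB cases, and "Number and proportion of pediatric patients on preventive treatment who completed therapy". Section IX compares pre- and post-intervention proportions by relative risk or risk difference with Z-tests. It provides no restriction or sensitivity analysis for baseline children whose courses ran past launch.

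**The concern.** A child who starts a 6-month course in the last months of the frame has an outcome that falls after the frame ends. The launch guard constrains the end of the frame, not the end of the course. If launch comes soon after the frame ends, that child spends part of the course, possibly most of it, at a site already running CaP TB. Section IV.A.2 lists components that could act on such a child or on how the outcome is recorded: SMS reminders and adherence strategies, mentorship, register training, and new tools for tracking preventive-therapy completion.

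The comparator for two key indicators would then have partly received the intervention. The exposure would also differ between sites, according to when each was launched and extracted. This is separate from whether follow-up is complete: every such child may have a fully observed outcome and still be exposed.

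**Working it through.** The plan gives no figure for this overlap, so there is none to reproduce. The check is timeline arithmetic.

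**Inputs.** Frame length 12 months, course length 6 months, and a lag of at least 6 months to extraction (all V.A). Assumption not in the documents: treatment starts are spread evenly over the frame.

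**Reading of the frame.** Taken literally, 12 months that start 6 months before extraction would run 6 months past extraction, which retrospective data cannot do. The workable reading is a window from 18 to 6 months before extraction.

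**Formulas.** Let g be the months from frame end to launch. A child who starts u months before frame end (u even on 0 to 12) finishes 6 - u months after frame end, and so has max(0, 6 - u - g) months under CaP TB.

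- Share of cohort with any overlap = max(0, 6 - g) / 12.
- Share of treatment time under CaP TB = [max(0, 6 - g)² / (2 × 12)] / 6 = max(0, 6 - g)² / 144.

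| g (months) | Any overlap | Treatment time |
|---|---|---|
| 6 or more | 0% | 0% |
| 5 | 1/12 = 8.3% | 1/144 = 0.7% |
| 4 | 2/12 = 16.7% | 4/144 = 2.8% |
| 3 | 3/12 = 25% | 9/144 = 6.3% |
| 2 | 4/12 = 33.3% | 16/144 = 11.1% |
| 1 | 5/12 = 41.7% | 25/144 = 17.4% |
| near 0 | 6/12 = 50% | 36/144 = 25% |

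A simulation at g = 0 gave 0.4996 and 0.2500.

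**Three situations under the text.**

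1. *Extraction at or before launch.* The frame ends at least 6 months before extraction, so g is at least 6 and overlap is zero.
2. *Extraction x months after launch, default frame (x up to 6).* Here g = 6 - x. At x = 1 the shares are 8.3% and 0.7%; at x = 2 they are 16.7% and 2.8%.
3. *Exception.* Interventions began during the default frame, so launch was more than 6 months before extraction. The frame is moved back until it ends before launch, with no minimum gap. At g near 0 the shares are 50% and 25%.

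**Effect on a comparison (illustration only).** Assume a true gain of 10 points in completion. At g near 0 the observed gain is 10 × (1 - 0.25) = 7.5 points if benefit is proportional to exposed course time, or 10 × (1 - 0.50) = 5 points if any overlap gives full benefit. At g = 4 the same two models give 10 × (1 - 0.028) = 9.7 and 10 × (1 - 0.167) = 8.3 points.

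**The case against.** The strongest reply is that the 6-month lag already does the work. With extraction at or before launch, every baseline course is due to end before CaP TB begins. A reader might infer that late starters in every site's baseline are contaminated; the documents do not support that. This part of the objection stands and limits the point to sites extracted after launch.

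Other parts also stand:

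- A reader might take the six to ten weeks in Table 3 as the delay between launch and extraction, giving about 2 months and 17%. That figure is how long collection takes across a country's sampled sites. The x = 2 row above is illustrative only.
- The 50% is an upper bound, not an estimate. It needs a frame ending just before launch. The plan gives neither the gap nor the number of exception sites.
- Benefit to children already mid-course is assumed. Section IV.A.2 says packages vary by country, and the expected effects in Sections III and IX concern case detection and preventive-therapy starts, not completion.
- If CaP TB improves completion, this mechanism dilutes the effect and cannot create a false benefit. The pre/post comparison is a secondary objective (II.B.2), although the goal in II.A also names it.

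One part does not stand. The end date of abstraction could be read as the end of the fieldwork, in which case all outcomes would be recorded before launch. But IV.A.3 and V.A allow the fieldwork after launch, and the exception makes sense only if the rule concerns the period covered. That exception also implies extraction more than 6 months after launch, which sits badly with extraction immediately after it; the two statements need reconciling.

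**Conclusion.** The point holds in a conditional form. No provision requires baseline courses to end before launch, so the rule in V.A does not secure its stated aim for treatment success and preventive-therapy completion at sites extracted after launch. Overlap is zero when extraction is at or before launch and small when it follows shortly after. In the plan's own exception it can reach 50% of the cohort and 25% of treatment time.

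These shares rest on even enrolment and 6-month courses. The overall bias cannot be computed, because the number of affected sites and their gaps are not given. The attenuation figures rest on an assumed 10-point gain. Indicators fixed at screening, diagnosis or treatment start are not affected by this mechanism.

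**What to change.** Add to V.A, for treatment success and preventive-therapy completion only:

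*The baseline numerator and denominator are limited to children whose course was due to end before the site's first CaP TB activity, that is, who started at least 6 months (or the planned duration of their regimen) before that date. The unrestricted 12-month cohort is reported as a sensitivity analysis.*

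Keep the full 12-month frame for all other indicators. Record each site's frame end, extraction date and launch date, and report how many sites have a gap under 6 months. In the same edit, state the frame as a window before extraction and reconcile the exception with the stated timing of extraction.

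**Cost.** A date filter that can be applied at analysis. DS-TB start dates are already needed for the time-to-treatment indicator; preventive-therapy start dates would come from the register already listed in Table 1. At affected sites the restricted baseline keeps 6 + g of the 12 months of starts, so the denominator falls by up to half. It then covers less than a full calendar year, with possible seasonal imbalance. Some clinics will have few children, since Table 3 expects at least 5 with presumptive TB per clinic. Moving the frame further back would avoid that loss but may need new register extraction, so it should be optional and only where abstraction is not yet done.
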